5.4. Investigational Product Storage

The Investigator, or an approved representative, eg, pharmacist, will ensure that all investigational products are stored in a secured area with controlled access under required storage conditions and in accordance with applicable regulatory requirements.

Site systems must be capable of measuring and documenting (for example, via a log), at a minimum, daily minimum and maximum temperatures for all site storage locations (as applicable, including frozen, refrigerated and/or room temperature products). This should be captured from the time of investigational product receipt throughout the study. Even for continuous monitoring systems, a log or site procedure that ensures active daily evaluation for excursions should be documented. The operation of the temperature monitoring device and storage unit (for example, refrigerator), as applicable, should be regularly inspected to ensure it is maintained in working order.

Any excursions from the product label storage conditions should be reported upon discovery. The site should actively pursue options for returning the product to the storage conditions as described in the labeling, as soon as possible. Deviations from the storage requirements, including any actions taken, must be documented and reported to the Sponsor.

Once an excursion is identified, the investigational product must be quarantined and not used until the Sponsor provides documentation of permission to use the investigational product. It will not be considered a protocol deviation if the Sponsor approves the use of the investigational product after the temperature excursion. Use of the investigational product prior to Sponsor approval will be considered a protocol deviation.

Specific details regarding information the site should report for each excursion will be provided to the site.

5.5. Investigational Product Accountability

The investigative site must maintain adequate records documenting the receipt, use, loss, or other disposition of all investigational product supplies.

5.5.1. Destruction of Investigational Product Supplies

The Sponsor or designee will provide guidance on the destruction of unused investigational products (eg, at the site). If destruction is authorized to take place at the study site, the investigator must ensure that the materials are destroyed in compliance with applicable environmental regulations, institutional policy, and any special instructions provided by Pfizer, and all destruction must be adequately documented.

5.6. Concomitant Medications

Medications or vaccinations specifically prohibited in the exclusion criteria are also not allowed during the active treatment period, except for administration of the inactivated influenza vaccine. Because multiple novel combinations will be explored during this study, live vaccines are not allowed during the active treatment period and for 90 days after the last dose of study treatment.

If there is a clinical indication for one of these or other medications or vaccinations specifically prohibited during the trial, discontinuation from study therapy or medication/vaccination may be required. The final decision on any supportive therapy or vaccination rests with the Investigator and/or the patient's primary physician. However, the decision to continue the patient on study therapy or medication/vaccination schedule requires the mutual agreement of the Investigator, the Sponsor, and the patient.

Concomitant treatment considered necessary for the patient's wellbeing may be given at discretion of the treating physician.

Concomitant medications and treatments, including herbal supplements, will be recorded from 28 days prior to the start of study treatments and up to 90 days after the last dose of study treatment. All concomitant medications should be recorded in the CRF including supportive care drugs (eg, antiemetic treatment and prophylaxis), and the drugs used to treat adverse events or chronic diseases, and non-drug supportive interventions (eg, transfusions). Concomitant treatments will not be collected for patients who initiate subsequent anticancer therapy.

Concurrent anticancer therapy with agents other than study treatments is not allowed. Medications intended solely for supportive care (eg, antiemetics, analgesics, megestrol acetate for anorexia) are allowed.

Recommended medications to treat infusion-related reactions, hypersensitivity reactions and flu-like symptoms, tumor lysis syndrome and immune-related events are reported in [Section 5.3.7.3.1](#), [Section 5.3.7.3.2](#), [Section 5.3.7.3.3](#), and [Section 5.3.7.3.4](#), respectively.

5.6.1. Hematopoietic Growth Factors

Primary prophylactic use of granulocyte-colony stimulating factors is not permitted during Cycle 1 of treatment, but they may be used to treat treatment emergent neutropenia as indicated by the current American Society of Clinical Oncology (ASCO) guidelines.²²

In subsequent cycles, the use of hematopoietic growth factors is at the discretion of the treating physician in line with local guidelines. Patients who enter the study on stable doses of erythropoietin or darbepoietin may continue this treatment, and patients may start either drug during the study at the discretion of the treating physician.

5.6.2. Concomitant Surgery

Caution is advised on theoretical grounds for any surgical procedures during the study. The appropriate interval of time between surgery and administration of investigational products required to minimize the risk of impaired wound healing and bleeding has not been determined. In case of a surgical procedure, investigational products should be delayed. Postoperatively, the decision to reinitiate investigational products should be discussed with the Sponsor.

5.6.3. Concomitant Radiotherapy

Palliative radiotherapy to specific sites of disease is permitted if considered medically necessary by the treating physician. All attempts should be made to rule out disease progression in the event of increased localized pain. If palliative radiotherapy is needed to control bone pain, the sites of bone disease should be present at baseline, otherwise, bone pain requiring radiotherapy will be considered as a sign of disease progression. Study treatment should be withheld for the entire duration of palliative radiotherapy and can be restarted upon recovery from any radiotherapy-related toxicities, but no sooner than 48 hours after radiotherapy completion.

5.6.4. Other Prohibited Concomitant Medicines and Therapies

Patients are prohibited from receiving the following therapies during the treatment phase of this trial:

- Anti-cancer systemic chemotherapy or biological therapy.
- Immunotherapy not specified in this protocol.
- Investigational agents other than investigational products.
- Radiation therapy (with the exception noted above in the Concomitant Radiotherapy Section 5.6.3).
- Immunosuppressive drugs, unless otherwise indicated for the treatment of irAEs (see Table 25. below Clarification Regarding Steroid Use).
- Other experimental pharmaceutical products.
- Any vaccine therapies for the prevention of infectious disease (eg, human papilloma virus vaccine) except for inactivated vaccines (eg, influenza vaccine).
- Herbal remedies with immunostimulating properties (eg, mistle toe extract) or known to potentially interfere with major organ function (eg, hypericin).

Combination F:

- Agents known to have TLR9 antagonist activity are prohibited throughout the study. The known antagonists are chloroquine, hydroxychloroquine, and quinacrine.

Clarifications Regarding Steroid Use: Data indicate that corticosteroids have an adverse effect on T-cell function and that they inhibit and damage lymphocytes.^{23,24} Furthermore, as with all immunotherapies intended to augment T-cell-mediated immunity, there is a risk that concomitant immunosuppressives such as steroids will counteract the intended benefit. However, studies with anti-CTLA-4 compounds indicate that short term use of steroids can be employed without compromising clinical outcomes.²⁵ Therefore, the use of steroids during this trial is restricted as follows:

- Therapeutic use: for the treatment of infusion-related reactions and short-term treatment of irAEs, steroids are permitted according to the modalities indicated in [Table 25](#).
- Therapeutic use for treatment of CRS as specified in [Section 5.3.7.3.3](#) is permitted.
- Stress dose steroids to prevent severe CRS in patients enrolled in Combination F as specified in [Section 5.3.5.2](#).
- Physiologic use: replacement for adrenal insufficiency at doses equivalent to ≤ 10 mg prednisone daily are acceptable. Higher doses of corticosteroids may be allowed for patients with a previous diagnosis of adrenal insufficiency. Sponsor consultation is required prior to enrollment to Combination F of a patient with adrenal insufficiency.
- Prophylactic use: prophylactic use, eg, for the prevention of acute infusion-related reactions, constitutes concomitant use and is prohibited except stress steroids to prevent severe CRS reactions in patients enrolled into Combination F as specified in [Section 5.3.5.2](#).
- Intranasal, inhaled, topical steroids, or local steroid injections (eg, intra-articular injection) are permitted.
- There are no prohibited therapies during the Post-Treatment Follow-up Phase.

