The Schedule of Activities table provides an overview of the protocol visits and procedures. Refer to the [ASSESSMENTS](#) section of the protocol for detailed information on each assessment required for compliance with the protocol.

The Investigator may schedule visits (unplanned visits) in addition to those listed in the Schedule of Activities table in order to conduct evaluations or assessments required to protect the well-being of the patient.

Table 3. Schedule of Activities: Combination A (Avelumab and Utomilumab) - Safety and Efficacy Assessments (Phase 1b and Phase 2)

Protocol Activities	Screening ^[1] ≤28 Days prior to Randomization/First dose	On Treatment (1 Cycle=28 Days)														End of Treatment/Withdrawal ^[38]	Post Treatment Follow-Up 90 days after last dose (Day 30, Day 60, Day 90) ^[39]		
		CYCLE 1				CYCLE 2				CYCLES 3-23				CYCLES ≥24					
		Day 1	Day 8	Day 15	Day 22	Day 1	Day 8	Day 15	Day 22	Day 1	Day 8	Day 15	Day 22	Day 1	Day 15				
Visit Time Window (days)			(±) 2	(±) 2	(±) 2	(±) 2	(±) 2	(±) 2	(±) 2	(±) 2	(±) 2	(±) 2	(±) 2	(±) 7	(±) 7	(+) 7	(±) 3		
Informed Consent ^[2]	X																		
Tumor History ^[3]	X																		
Medical History ^[4]	X																		
Physical Examination ^[5]	X	X	X	X	X	X	X	X	X				X		As clinically indicated	X	X (Day 30)		
Baseline Signs & Symptoms ^[6]		X																	
ECOG PS ^[7]	X	X				X				X						X	X (Day 30)		
Vital Signs ^[8]	X	X	X	X	X	X	X	X	X		X		X	X	X		X (Day 30)		
Contraceptive Check ^[9]	X	X			X				X				X		X		X (Day 90)		
Safety Labs/Measurements																			
Hematology ^[10]	X	X	X	X	X	X	X	X	X		X		X	X	X		X (Day 30)		
Blood Chemistry ^[11]	X	X	X	X	X	X	X	X	X		X		X	X	X		X (Day 30)		
Coagulation ^[12]	X	X														As clinically indicated			
Urinalysis ^[13]	X															As clinically indicated			
Serum/Urine Pregnancy Test ^[14]	X	X		X		X		X		X		X		X	X	X	X (Day 30)		
12-Lead ECG ^[15]	X	X				X										X			
HBV, HCV tests ^[16]	X																		
ACTH and Thyroid Function Tests ^[17]	X															C3 then every 12 wks.	X		
Registration and Treatment																			
Randomization/Enrollment ^[18]		X																	

Protocol Activities	Screening ^[1] ≤28 Days prior to Randomization/ First dose	On Treatment (1 Cycle=28 Days)														Post Treatment			
		CYCLE 1				CYCLE 2				CYCLES 3-23				CYCLES ≥24					
		Day 1	Day 8	Day 15	Day 22	Day 1	Day 8	Day 15	Day 22	Day 1	Day 8	Day 15	Day 22	Day 1	Day 15				

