6.3. Follow-up

For follow-up procedures see the [Schedule of Activities](#) and Assessments section ([Section 7](#)).

Patients should be evaluated up to 90 days (30 days, 60 days, and 90 days) after last dose of investigational product(s) for safety. Patients continuing to experience toxicity following discontinuation of investigational products will continue to be followed at least every 4 weeks regardless of initiation of new anticancer treatment until resolution or determination, in the clinical judgment of the Investigator, that no further improvement is expected. Follow-up beyond 30 days after last dose of investigational products product(s) may be performed either via a clinic visit or by remote contact (eg, telephone), with subsequent clinic visits requested if any concerns are noted during the telephone call.

Physical examination, ECOG status, vital signs, and safety laboratory measurements are not required for patients who initiate new anticancer treatment, unless the patient continues to experience toxicity following discontinuation of the investigational products. Contraception check and serum/urine pregnancy tests are required for all patients who enter Follow-up regardless of initiation of subsequent anticancer therapy. Patients whose disease has not progressed at the time of treatment discontinuation will enter into disease follow-up (for tumor assessment).

Patients will be followed for survival, independently of time of disease progression or initiation of subsequent anticancer therapy, for at least 2 years after randomization of the last patient in the randomized cohorts and for at least 2 years after first dose of the last patient for the non-randomized cohorts unless lost to follow-up, consent withdrawal, or study discontinued by the Sponsor. Patients will be contacted every 3 months for survival status and subsequent anticancer treatment.

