8.2. Reporting Period

For SAEs, the active reporting period to Pfizer or its designated representative begins from the time that the subject provides informed consent, which is obtained prior to the subject's participation in the study, ie, prior to undergoing any study-related procedure and/or receiving investigational product, through and including 90 calendar days after the last administration of the study treatment.

SAEs occurring to a subject after the active reporting period has ended should be reported to the sponsor if the investigator becomes aware of them; at a minimum, all SAEs that the investigator believes have at least a reasonable possibility of being related to study treatment are to be reported to the sponsor.

AEs (serious and non-serious) should be recorded on the case report form (CRF) from the time the subject has taken at least 1 dose of study treatment through 90 calendar days after the last administration of the study treatment.

If a patient begins a new anticancer therapy, the AE reporting period for non-serious AEs ends at the time the new treatment is started. Death and SAE must be reported if it occurs during the SAE reporting period after the last dose of study treatment, irrespective of any intervening treatment.

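### Section 5.6 bans live vaccines for 90 days after the last dose, but the closing bullet of Section 5.6.4 lifts all prohibitions over the same 90 days

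*Protocol*

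**What the plan says.** Four places in the protocol bear on vaccination or on prohibited therapy after treatment ends.

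- **Section 5.6 (Concomitant Medications)** gives a live-vaccine rule with a stated period: "live vaccines are not allowed during the active treatment period and for 90 days after the last dose of study treatment". Its stated reason is that several novel combinations are being explored.
- **Section 5.6.4 (Other Prohibited Concomitant Medicines and Therapies)** opens its list with "Patients are prohibited from receiving the following therapies during the treatment phase of this trial". One item on that list is "Any vaccine therapies for the prevention of infectious disease (eg, human papilloma virus vaccine) except for inactivated vaccines (eg, influenza vaccine". The section then gives clarifications on steroid use, and the last bullet there reads "There are no prohibited therapies during the Post-Treatment Follow-up Phase".
- **Section 4.2, exclusion criterion 16** prohibits vaccination around the first dose and while the patient is on trial, except with inactivated vaccines. It does not say whether follow-up counts as being on trial.
- **Section 5.6.4, Combination F item**, states: "Agents known to have TLR9 antagonist activity are prohibited throughout the study".

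The follow-up period is described in the Schedule of Activities, where the Combination A safety table (Table 3) heads the column "Post Treatment Follow-Up 90 days after last dose (Day 30, Day 60, Day 90", and in Section 6.3: "Patients should be evaluated up to 90 days (30 days, 60 days, and 90 days) after last dose of investigational product(s) for safety".

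**The concern.** Take a patient 45 days after the last dose for whom a live vaccine is being considered. Section 5.6 says it is not allowed. Section 5.6.4, read as worded, says nothing is prohibited at that time. Both sections are natural places for a site to look, and neither refers to the other on this point.

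The restriction is a safety measure that the protocol itself justifies. The same window is the active reporting period for serious adverse events, which under Section 8.2 runs "through and including 90 calendar days after the last administration of the study treatment". Some patients who stopped treatment for immune-related events could still be on high-dose steroids or a taper under Table 25 during this time. If a live vaccine were given, its status as a protocol deviation would depend on which section was read, and a later event would be harder to interpret. Causality has to be assessed for every adverse event in any case (Section 8.9), so the need for attribution is not a separate harm.

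**Working it through.** No formula applies and there is no plan figure to reproduce. The check sets the passages side by side and compares the periods they cover.

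| Source | What it covers | Period after the last dose |
|---|---|---|
| Section 5.6 | Live vaccines prohibited | 0 to 90 days |
| Section 5.6.4, list of prohibited therapies | Non-inactivated vaccines prohibited | None (treatment phase only) |
| Section 5.6.4, last bullet | No therapy prohibited | Post-treatment follow-up |
| Section 4.2, criterion 16 | Vaccines other than inactivated prohibited while on trial | Not defined |
| Schedule of Activities, Table 3; Section 6.3 | Post-treatment safety follow-up | To 90 days, with Days 30, 60 and 90 |
| Section 8.2 | Serious adverse event reporting | To 90 days |

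1. **Overlap.** If follow-up is counted from the last dose, it covers 90 of the 90 days of the post-treatment ban. If it is counted from the end-of-treatment visit, the overlap is shorter only by the days between the last dose and that visit. Essentially the whole post-treatment part of the ban is affected.
2. **Whether Section 5.6.4 carries the 90-day rule elsewhere.** It does not. Its vaccine item ends with the treatment phase, and the section neither makes an exception for live vaccines nor refers back to Section 5.6.
3. **Whether another rule settles it.** The protocol states no order of precedence between its sections. Criterion 16 would support the restriction if follow-up counts as being on trial, but that phrase is not defined.
4. **TLR9 antagonists.** The Combination F ban is worded as lasting for the whole study, yet it sits in a section whose opening limits its prohibitions to the treatment phase. No period after the last dose is given. Its end point is therefore unclear.

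**The case against.** The strongest answer is context. The sentence is the final bullet of a list headed as clarifications on steroid use, and every other bullet there concerns steroids. It may have been meant only to end the steroid restrictions, or to close a list that applies to the treatment phase. That is plausible, and it makes a drafting slip more likely than a deliberate change of rule. It does not remove the conflict, because the sentence speaks of therapies in general. If steroids alone were meant, the wording still needs correcting.

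A second answer is that Section 5.6 should govern. It names the product, the period and the reason, whereas the bullet never mentions vaccines, and the heading of Section 5.6.4 suggests that it adds to Section 5.6. This stands as far as it goes. A reader might infer that Section 5.6.4 cancels the 90-day rule because it is the later or more specific text. The protocol does not support that: on live vaccines Section 5.6 is the more specific text, and no rule of precedence makes either section override the other. For the same reason, a site has to infer for itself that Section 5.6 prevails.

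Section 5.6 also has a route for agreeing individual cases between the investigator, the sponsor and the patient. That text concerns continuing study therapy or a vaccination schedule and does not reconcile the statement about follow-up.

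**Conclusion.** The point holds as an internal inconsistency: the protocol is wrong as written. Read literally, Sections 5.6 and 5.6.4 give opposite instructions on live vaccines for essentially the whole 90 days after the last dose. This rests on taking the Post-Treatment Follow-up Phase to include the period so labelled in the Schedule of Activities, and on reading the bullet as worded.

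Two stronger readings are not supported. A reader might infer that every patient in every combination is affected. The text covers all of them, but it matters only for those for whom a live vaccine is considered in the window, and that number cannot be derived. Further enrollment in Combinations A and B is not planned, Phase 2 of Combinations C and D is not planned, and the protocol does not say how many of those patients still have the window ahead. A reader might also infer a second contradiction of equal weight over TLR9 antagonists. The surrounding limit to the treatment phase makes that an ambiguity only.

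No endpoint, dose-limiting toxicity window, analysis set, sample size or primary analysis is affected. The correction should be made because the restriction concerns safety. Which rule is clinically right is not judged here.

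**What to change.** Reconcile Section 5.6, both the prohibited list and the last bullet of Section 5.6.4, and exclusion criterion 16, so that one live-vaccine rule applies after the last dose. The sponsor decides which rule stands. For example, the bullet could be limited to what it was meant to cover or could cross-refer to Section 5.6, and criterion 16 could say whether being on trial includes follow-up. In the same edit, state whether the Combination F ban on TLR9 antagonists ends with treatment or continues into post-treatment follow-up.

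The cost is about one sentence, with small matching edits, in an amendment or administrative change letter. Sample size and planned analyses are unchanged.

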5.7. Rescue Medications and Supportive Care

5.7.1. Supportive Care Guidelines

Patients should receive appropriate supportive care measures as deemed necessary by the treating Investigator including but not limited to the items outlined below:

- Diarrhea: All patients who experience diarrhea should be advised to drink liberal quantities of clear fluids. If sufficient oral fluid intake is not feasible, fluid and electrolytes should be substituted via IV infusion.
- Nausea/Vomiting: Nausea and vomiting should be treated aggressively, and consideration should be given in subsequent cycles to the administration of prophylactic antiemetic therapy according to standard institutional practice. Patients should be strongly encouraged to maintain liberal oral fluid intake.
- Anti-infectives: Patients with a documented infectious complication should receive oral or IV antibiotics or other anti-infective agents as considered appropriate by the treating Investigator for a given infectious condition, according to standard institutional practice. Prophylactic administration should be considered for the cases outlined in [Table 25](#).
- Anti-inflammatory or narcotic analgesics may be offered as needed.

- Patients who need to be on anticoagulant therapy during treatment should be treated with low molecular weight heparin. If low molecular weight heparin cannot be administered, coumadin or other coumarin derivatives or other anti-coagulants (including direct Xa inhibitors) may be allowed; however, appropriate monitoring of prothrombin time/international normalized ratio (PT/INR) should be performed.

